## **6.8. Protocol Permitted Substitutions**

### **6.8.1. Oral Bridging**

In exceptional circumstances, to address pre-planned missed CAB LA + RPV LA dosing visits, in consultation with the medical monitor, Investigators may provide daily oral CAB 30 mg and RPV 25mg as a short-term “bridging” strategy for participants who have begun CAB LA + RPV LA. In certain circumstances (e.g., prior to steady state dosing and following a >4 week oral bridge) repeating the loading doses of CAB IM and RPV IM may be required. Should a participant require “oral bridging”, sites must contact the medical monitor for guidance with treatment and dosing strategies prior to a missed CAB LA + RPV LA dose.

## **6.9. Interruption of Study Treatment and Visit/Dosing Windows**

IP or current ART may be interrupted at the discretion of the Investigator in the event of an AE, according to the severity of the AE.

If one or more antiretroviral medications is held due to toxicity or adverse events, all antiretroviral medications must be held to reduce the risk of development of resistance taking into account both the length of the planned interruption and the pharmacokinetic half-life of each antiretroviral of the regimen, in a way to minimize the risk of development of resistance.

**It is important to note that keeping to the participant’s visit schedule is a very important component to the study.**

**Note: All decisions regarding dose interruption / resumption must be discussed with the medical monitor in advance.**

### **6.9.1. IM Dosing**

Participants receiving CAB LA and/or RPV LA are anticipated to be at risk for development of virologic resistance if ART is interrupted. The time period during which participants are at risk for development of virologic resistance may be determined by the period between when drug levels fall below therapeutic values and when they fall below levels which exert selective pressure on HIV. This time period will vary by ART agent and is dependent upon effective concentration, inhibitory concentration, and half-life. Plasma concentrations of both LA drugs may be measurable for more than one year following IM injections. Any interruption in IM dosing should be discussed with the Medical Monitor. Investigators should ensure that the participant initiates alternative highly active ART to minimize the risk of developing resistance as concentrations of CAB and RPV decline over time.

IM dosing is expected to occur during the week in which the participant’s projected visit falls (as according to the date of the first injection). The first injections are administered at Week 4b (can be performed as soon as lab results from Week 4a become available), and the second injections are given at Week 8. The dosing window for the second injections allows administration between Week 7 and Week 8, but not later than Week 8. The dosing window for the third injections allows administration between Week 11 and

Week 12 but not later than Week 12. For subsequent injection visits, an additional (+ or -) 7 day window, from the projected visit date, is allowable for IM dosing but also not preferred. In addition, starting after the Week 12 injection, efforts should be made to limit time between injection visits to a maximum of 5 weeks. The Medical Monitor must be contacted if the length of time between injections exceeds or is projected to exceed 5 weeks. For the duration of the study, the injection visit schedule should be maintained according to the first IM injections given at Week 4b.

For participants transitioning from current ART to IM dosing, the first injections are administered at Week 56b (can be performed as soon as lab results from the 56a visit become available), and the second injections are given at Week 60. The dosing window for the second injections allows administration between Week 59 and Week 60, but not later than Week 60. The dosing window for the third injections allow administration between Week 63 and Week 64, but not later than Week 64. For subsequent visits, a (+ or -) 7 day window, from the projected visit date, is allowable for IM dosing but also not preferred.

At the one-week post dose visits (Week 5 and Week 41), there is no defined visit window, rather visits should occur approximately one week from the last injection.

- Dosing may occur without consultation from the Medical Monitor if performed within the (+ or -) 7 day window.
- Any request for the visit/dosing to occur outside of the allowed window must be discussed and agreed with the Medical Monitor *prior* to dosing. In the event of a late dose, a revised dosing schedule for subsequent dosing may be required and will be communicated to the site staff at the time of approval for continued dosing. Temporary switch to oral dosing of CAB and/or RPV may be an option based on individual participant circumstance as described in Section 6.8.
- See the SPM for scheduling guidance and further information and examples.

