#### 4.7.3.1. CAB LA

For CAB LA, the model included data from 416 participants who received CAB LA IM as single or repeat administration, with approximately 50% of data obtained from 200056 (LATTE-2), ~20% from study 201120 (CAB LA pre-exposure prophylaxis [PrEP] study, GlaxoSmithKline Document Number 2015N229664\_00) and ~30% from Phase 1 studies). The simulation of the predicted median (90% prediction interval [PI]) CAB concentration-time profile based on the population PK model is shown in Figure 4. The lower bound of the PI remains approximately at or above 4x-PA-IC90 throughout dosing. At steady state, 98% of the population is predicted to achieve trough concentrations above 4x the - Protein adjusted 90% inhibitory concentration (PA-IC90), and 88% are predicted to achieve trough concentrations above the geometric mean trough following the 10mg oral dose in LATTE of 1.35µg/mL (8-fold PA-IC90).

**Figure 4 Simulated\* Median (90% Prediction Interval [PI]) CAB Plasma Concentrations versus Time for the CAB LA Q4W Regimen (600 mg IM Day 1, then 400mg IM Q4W)^**

Medium dashed line at 1.35 $\mu$ g/mL corresponds to the geometric mean Ctrough following oral CAB 10mg once daily (LATTE) and is equivalent to 8x PA-IC90

Dotted line at 0.664 $\mu$ g/mL corresponds to 4x PA-IC90

[figure not shown]
Long dashed line at 0.166  $\mu$ g/mL corresponds to the PA-IC90.

\*Note: current simulations based on interim plasma concentration dataset

^Study Time and Events include a 4 week oral lead in. Therefore, Day 1 = day of first injections (Week 4b study visit); Week 4 = second injections (Week 8 study visit)

At steady state, a one week delay in dosing of the Q4W regimen results in an approximately 15% reduction in median Ctrough. With this delay, 95% are predicted to remain above 4x PA-IC90, and 79% are predicted to remain above the 10mg oral target (Figure 5). Simulations including delays greater than one week have been explored (not shown), with <70% of subjects remaining above the 10mg oral target. Therefore, a 1-week delay is the maximum allowed per the protocol.

**Figure 5** Impact of a 1-week Delay in Dosing at Steady State (Week 40 delayed to Week 41) on Simulated\* Median (90% PI) CAB Plasma Concentrations versus Time for the CAB LA Q4W regimen (600mg IM Day 1, then 400mg IM Q4W thereafter)^

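### A Section 6.9.1 bullet clears dosing without Medical Monitor consultation anywhere in a plus-or-minus 7-day window, against the same section's 5-week contact rule and its no-late-dose windows for injections 2 and 3

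*Protocol*

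**What the plan says.** All the conflicting statements are in Protocol Section 6.9.1 (IM Dosing).

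- **Windows.** The second injections may be given from Week 7 to Week 8 and the third from Week 11 to Week 12, with nothing later than Week 8 or Week 12. Participants moving over from current ART have the matching limits of Week 60 and Week 64. From the fourth injection on, "an additional (+ or -) 7 day window, from the projected visit date, is allowable for IM dosing but also not preferred".
- **Anchor.** "For the duration of the study, the injection visit schedule should be maintained according to the first IM injections given at Week 4b". An early dose therefore does not move the next projected date.
- **Interval rule.** After the Week 12 injection, "efforts should be made to limit time between injection visits to a maximum of 5 weeks", followed by: "The Medical Monitor must be contacted if the length of time between injections exceeds or is projected to exceed 5 weeks".
- **Bullets at the end of the section.** The first reads "Dosing may occur without consultation from the Medical Monitor if performed within the (+ or -) 7 day window". The second covers the other case: "Any request for the visit/dosing to occur outside of the allowed window must be discussed and agreed with the Medical Monitor", and this must happen before dosing. Neither mentions the 5-week limit or the one-sided early windows.

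The 5-week contact rule also appears in the Synopsis (Overall Design, Maintenance Phase, Extension Phase) and in Sections 4.2.2 and 4.2.3.2. The paragraph in Section 6.9.1 for participants switching from current ART does not repeat it. Section 4.7.2 and the window note under Table 8 in Section 7.5.1 confirm that injections 2 and 3 have a minus-7-day window only.

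**The concern.** The two bullets are the short operational summary that a site coordinator is likely to work from, and they sort doses by window alone. Two kinds of dose are misdirected.

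The first is an in-window dose given more than 5 weeks after the previous one. The bullet clears it without consultation, although the section makes contact mandatory.

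The second is a second or third injection given up to 7 days late. It falls inside the bullet's symmetric window but outside the window that the section sets for that injection. If the allowed window in the second bullet means the window for that particular injection, the same dose is exempt under one bullet and needs prior agreement under the next.

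At stake is a safety contact that the protocol requires. Section 6.9.1 itself warns of resistance if ART is interrupted, and Section 4.7.3.1 limits dosing delay on pharmacokinetic grounds: "Therefore, a 1-week delay is the maximum allowed per the protocol".

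**Working it through.** **Inputs.** The nominal interval is 4 weeks, or 28 days (Section 4.2.2). The contact threshold is 5 weeks = 5 × 7 = 35 days (Section 6.9.1). Let d be the number of days from the projected date. The first injection is the anchor, d = 0. The section allows d = −7 to 0 for injections 2 and 3, and d = −7 to +7 from injection 4 on.

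**First conflict: the interval.** Because the dates stay anchored, the gap between consecutive injections is

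gap = 28 + d(later) − d(earlier).

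Counting every whole-day combination that the section's own windows allow:

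| Injections | Pairs | Longest gap (days) | Pairs over 35 days |
|---|---|---|---|
| 1 to 2 | 1 × 8 = 8 | 28 + 0 − 0 = 28 | 0 |
| 2 to 3 | 8 × 8 = 64 | 28 + 0 + 7 = 35 | 0 |
| 3 to 4 | 8 × 15 = 120 | 28 + 7 + 7 = 42 | 28 |
| later | 15 × 15 = 225 | 28 + 7 + 7 = 42 | 28 |

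A gap above 35 days needs d(later) − d(earlier) ≥ 8. With the earlier dose at −7, −6, …, −1 this leaves 7, 6, 5, 4, 3, 2 and 1 choices for the later dose, a total of 28. An earlier dose at 0 or later leaves none. The shares are 28/120 = 23.3% and 28/225 = 12.4% of allowed combinations. They are not expected frequencies.

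The first interval at which the conflict can arise is a third injection at Week 11 followed by a fourth at Week 17. Both are in window and they are 6 weeks, or 42 days, apart.

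**Second conflict: injections 2 and 3.** Read as written, the bullet covers d = +7 for these injections too. That means Week 9 instead of Week 8 at the latest, and Week 13 instead of Week 12. For switchers it means Week 61 instead of 60, and Week 65 instead of 64.

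An interval cap alone would not cure this. A second injection 7 days late comes 28 + 7 = 35 days after the first, which does not exceed 35. A third injection 7 days late after an on-time second also gives 28 + 7 = 35.

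**What the pharmacokinetic text adds.** Section 4.7.3.1 predicts steady-state CAB troughs above the 10 mg oral target in 88% of participants on schedule and in 79% after a one-week delay. Beyond that: "Simulations including delays greater than one week have been explored (not shown), with <70% of subjects remaining above the 10mg oral target". The delay shown there is a single scheduled dose moved from Week 40 to Week 41. An early dose followed by a late one, or a late second or third injection, is not modelled. The figures give a direction and no estimate for the gaps above.

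**The case against.** The strongest reply is that the section should be read as a whole. The 5-week rule is introduced as an addition to the window, uses mandatory language and is stated several times elsewhere. The bullet is permissive and expressly cancels nothing. A careful site would apply the stricter rule and would take the window for injections 2 and 3 from the paragraph above. On this view all that is missing is a cross-reference. It can also be said that consultation before dosing and contact about a long interval are different acts, and that the bullets send sites to the Study Procedures Manual, which is not shown, for scheduling examples.

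Much of this stands. The intent is clear, and whether any site would be misled cannot be judged from the protocol. It does not remove the defect. The bullet is a definite permission that covers doses for which the same section requires contact or forbids lateness, and a site acting on it would have no reason to call. A separate manual can explain the protocol, but it does not correct a conflicting sentence in it.

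A reader might go further and infer that the protocol sanctions unsupervised six-week gaps, or that the fall from 88% to 79% to below 70% measures the resulting loss of exposure. The documents support neither. The contact rule is stated repeatedly and never withdrawn, and Section 4.7.3.1 simulates a different situation.

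**Conclusion.** The inconsistency is real and minor. From the third-to-fourth interval onward, gaps of 36 to 42 days can arise with both doses in window. For these the bullet and the 5-week rule give opposite instructions. The bullet's symmetric window also does not respect the early-only windows for the second and third injections, in either arm. The excess over the contact threshold is at most 42 − 35 = 7 days, and the lateness at injections 2 and 3 is at most 7 days.

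The calculation assumes whole days, projected dates held to the first injection as Section 6.9.1 states, and 5 weeks meaning 35 days. How often such gaps would occur is unknown: the protocol calls use of the window not preferred and gives no rates. Sample size, alpha and the primary analysis are unaffected, so this is a matter of operational safety. It should be corrected because the correction is simple and the contact is one that the protocol itself requires.

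**What to change.** In the first bullet of Section 6.9.1, keep the opening permission and replace the window condition with:

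*within the allowed window for that injection (second and third injections: up to 7 days early, never late; later injections: plus or minus 7 days) and no more than 5 weeks (35 days) after the previous injection.*

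This cuts the longest in-window gap without consultation from 42 to 35 days, and the wording on each injection's own window closes the gap for injections 2 and 3 that a cap alone would leave. Repeating the 5-week sentence in the Section 6.9.1 paragraph for switchers is optional, because Section 4.2.3.2 already states it. Section 7.4.3.9 repeats the general window but refers to Section 6.9.1, so it need not change.

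The cost is one reworded bullet at the next amendment, with no change to design, visits or analysis.

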**Note: All decisions regarding dose interruption/ resumption must be discussed with the Medical Monitor in advance.**

### **6.9.2. Oral Dosing**

Visits for participants on the oral dosing arm are expected to occur as projected according to the Baseline visit. There is a (+ or -) 3 day visit window, from the projected visit date. However, the number of tablets dispensed should be considered when scheduling the next visit.

Any interruption in therapy (scheduling conflicts, life circumstances, etc) during any oral dosing period that is greater than 7 consecutive days must be discussed with the Medical Monitor prior to resumption of therapy. The Medical Monitor must be contacted upon site staff becoming aware of resumption in therapy, if therapy was resumed without prior approval.

Visits for participants in Long Term Follow Up are expected to occur as projected according to the last injection.

## 6.10. Discontinuation of Study Treatment

Participants unable to manage drug toxicity or tolerate investigational product (IP, either formulations of CAB or RPV) must have IP discontinued. Any participant receiving at least one dose of CAB LA and /or RPV LA who discontinue IP / Withdraw will initiate treatment with HAART enter the Long-Term Follow-Up Phase for 52 weeks of follow up (see Section 4.2.4).

## 6.11. Treatment of Study Treatment Overdose

For participants receiving Oral CAB, any tablet intake exceeding a total daily dose of 30 mg will be considered an overdose. For participants receiving oral RPV, any dose exceeding a total daily dose of 25 mg will be considered an overdose.

For CAB LA and RPV LA, any single dose in excess of the studied doses will be considered an overdose.

Should IM maladministration, specifically overdose or inadvertent IV dosing, be suspected at any time, the participant will stay onsite for approximately 2-3 hours post dose for safety monitoring and an ECG will be performed at 2 hours post dose. The Medical Monitor will be notified in the event of a suspected maladministration.

In the event of suspected maladministration, additional PK samples will be drawn at 2 hours post dosing for evaluation of CAB and RPV concentrations.

For the purposes of this study, an overdose is not an AE (refer to Section 12.6.1 ) unless it is accompanied by a clinical manifestation associated with the overdose. If the clinical manifestation presents with serious criteria, the event is a SAE (see Section 12.6.2).

If an overdose occurs and is associated with an adverse event requiring action, all study medications must be temporarily discontinued until the adverse event resolves.

The Investigator should use clinical judgement in treating overdose, as ViiV Healthcare is unable to recommend specific treatment.

In the event of an overdose the investigator or treating physician should:

1. Contact the Medical Monitor immediately
2. Closely monitor the participant for adverse events (AEs)/serious adverse events (SAEs) and laboratory abnormalities until the IP can no longer be detected systemically (at least 5 days for oral CAB and oral RPV, and 52 weeks for CAB LA and RPV LA)
3. Obtain a plasma sample for pharmacokinetic (PK) analysis if possible within 2 days from the date of the last dose of study treatment if requested by the Medical Monitor (determined on a case-by-case basis).
4. Document the quantity of the excess dose as well as the duration of the overdosing in the CRF.

Decisions regarding dose interruptions or modifications will be made by the investigator in consultation with the Medical Monitor based on the clinical evaluation of the participant.

## **6.12. Treatment After the End of the Study**

The investigator is responsible for ensuring that consideration has been given to the post-study care of the participant's medical condition, whether or not GSK is providing specific post-study treatment. Participants who have successfully completed 96 weeks of treatment will continue to have access to both CAB LA and RPV LA in the Extension Phase until study treatment is either locally approved and commercially available, the participant no longer derives clinical benefit, the participant meets a protocol-defined reason for discontinuation or until development of either CAB LA or RPV LA is terminated.

## **6.13. Concomitant Medications and Non-Drug Therapies**

Participants must be advised to notify their Investigator of any current or proposed concomitant medication, whether prescribed or over-the-counter, because of the potential for interactions between such treatments and the study medications. Concomitant medications (prescription and non-prescription) will be permitted during the course of the study at the investigator's discretion (except for prohibited medications described in Section 6.13.2) and should be administered only as medically necessary during the study. All concomitant medication, blood products, and vaccines taken during the study will be recorded in the eCRF. The minimum requirement is that the drug name, route, and the dates of administration are to be recorded.

### **6.13.1. Permitted Medications and Non-Drug Therapies**

Chemoprophylaxis for HIV-associated conditions is encouraged, if appropriate, at the discretion of the participant and their physician. All concomitant medications, blood products, and vaccines taken during the study will be recorded in the eCRF with dates of administration.

Because non-HIV vaccines may cause a temporary increase in the level of plasma HIV-1 RNA, it is recommended that a vaccine, if necessary, be given during or immediately after a scheduled visit after all laboratory tests have been drawn. This approach will minimize the risk of non-specific increases in the level of plasma HIV-1 RNA at the next scheduled assessment.

Other IM injectables (with exceptions below) are permitted but must be administered away from the site of IP administration (should be spaced 2 cm or more away from site of IP injection).

#### **Antacid and H2 Antagonist Use:**

While both oral CAB and RPV have dosing requirements with antacid products containing divalent cations, only oral RPV has requirements for dosing with H2

antagonists. Since co-administration of oral CAB and RPV is required in this study, the most restrictive dosing requirements must be taken into consideration.

**CAB oral administration only:** Antacid products containing divalent cations (e.g., aluminium, calcium and magnesium) must be taken at least 2 hours before or at least 4 hours after CAB.

Concurrent administration of multivitamins is acceptable.

**RPV oral administration only:** Antacid products containing divalent cations (e.g., aluminium, calcium and magnesium) must be taken at least 2 hours before or at least 4 hours after RPV. H2-Receptor antagonists (e.g. cimetidine, famotidine, nizatidine, ranitidine) may cause significant decreases in RPV plasma concentrations. H2-receptor antagonists should only be administered at least 12 hours before or at least 4 hours after RPV. RPV should not be co-administered with proton pump inhibitors, such as esomeprazole, lansoprazole, omeprazole, pantoprazole, rabeprazole.

**RPV:** Administration of clarithromycin, erythromycin and telithromycin is not recommended with RPV due to possible increase in plasma concentration of RPV due to CYP3A enzyme inhibition. Where possible, alternatives such as azithromycin should be considered. Please refer to the local rilpivirine prescribing information for guidance regarding other drugs that are prohibited, should be used with caution, require dose adjustment, or increased clinical monitoring if taken with rilpivirine.

Drugs that cause Torsade des Pointes (TdP) should be used with caution when on rilpivirine (see SPM for list of drugs associated with TdP).

### 6.13.2. Prohibited Medications and Non-Drug Therapies

The following concomitant medications or therapies are not permitted at any time during the study:

- HIV immunotherapeutic vaccines are not permitted at any time during the study.
- Other experimental agents, antiretroviral drugs not otherwise specified in the protocol, cytotoxic chemotherapy, or radiation therapy may not be administered (see Exclusion Criteria #32, Section 5.2).
- Systemically administered immunomodulators (such as interleukin and interferon agents) are prohibited (a list of examples is provided in the SPM). This includes topical agents with substantial systemic exposure and systemic effects. Use of topical imiquimod is permitted.
- Acetaminophen (paracetamol) cannot be used in patients with acute viral hepatitis (James, 2009).
- Chronic use of systemic (oral or parenteral) glucocorticoids must be avoided due to their immunosuppressive effect and potential decreases in RPV plasma concentrations; however, short treatment courses with oral prednisone/prednisolone/methylprednisolone (e.g. adjunctive treatment of Pneumocystis pneumonia with  $\leq 21$  days of tapering prednisone) are allowed. A single dose of

systemic dexamethasone is permitted (more than a single dose in a treatment course may cause significant decrease in RPV plasma concentration and is prohibited). Topical, inhaled or intranasal use of glucocorticoids will be allowed.

- Hepatitis C infection therapy is prohibited during the Maintenance Phase before the Week 48 primary endpoint, and interferon-based HCV therapy or use of any drugs that have a potential for adverse drug:drug interactions with study treatment is prohibited throughout the entire study.

For information on concurrent therapies and interactions suspected to be relevant to other antiretroviral therapy in the regimen, please consult the local prescribing information.

